### **11.3.3 Decided by the sponsor**

The Sponsor could decide premature discontinuation of the study in the following cases:

- The study is not conducted in accordance with the procedures defined in the approved protocol (i.e., low rate of recruitment - protocol deviations - failure to ensure the quality of the data collected).
- Information on the Investigational Product (IP) that could change the current benefit-risk profile of the IP or that would be sufficient to require changes in the IP administration or in the overall conduct of the trial.
- The total number of subjects included earlier than expected.

- Discontinuation recommended by the DMC after a GST interim look in case of futility or because of efficacy of the highest tested dose (see Statistical considerations)
- Unexpected events that could jeopardize the conduct and quality of the study. These events could be any of the followings: Conflicts in a specific country, Major climatic reasons or earthquakes, Unexpected epidemics (eg. SRAS), Financial issues (funding does not match the incurring costs), External constraints that could prevent IP distribution etc....External events not yet identified.

In any case, the exact reason of termination will be specified and the ethics committee informed within 15 days after the decision is taken.

#### **11.3.4 Decided by the investigator**

The Investigator could stop the research if in his judgment the participating subjects are exposed to risks that are not ethically or scientifically justifiable and must notify in writing the Sponsor of this decision providing the reason thereof.

In all cases IEC/IRBs and Health Authorities should be informed by sponsor, within 15 days after the decision was taken.

## 12 SAFETY

### 12.1 Definitions

#### 12.1.1 Adverse event (AE)

An AE is any untoward medical event in a patient or clinical investigation subject administered a pharmaceutical product. An AE does not necessarily have to have a causal relationship with this treatment. An AE can therefore be any unfavourable and unintended sign (including abnormal laboratory finding), symptom, or disease temporally associated with the use of a medicinal (investigational) product, whether or not considered related to the medicinal (investigational) product.

**Lack of efficacy unless considered serious, should not be reported as adverse event. The Pure tone audiometry assessment is part of the efficacy assessment, as well as the administration of rescue treatment.**

#### 12.1.2 Serious adverse event (SAE)

A Serious AE is any untoward medical occurrence that at any dose:

- Results in death - Includes all deaths, even those that appear to be completely unrelated to study drug (e.g., car accident where subject is a passenger).
- Is life-threatening - In the view of the Investigator, the subject is at immediate risk of death at the time of the event. This does not include an AE that had if occurred in a more severe form, might have caused death.
- Requires in-patient hospitalisation or prolongation of existing hospitalisation. Prolongation of existing hospitalisation is defined as hospital stay longer than originally anticipated for the event or development of a new AE as determined by the Investigator or treating physician
- Results in persistent or significant disability/incapacity (substantial disruption of one's ability to conduct normal life functions).
- Is a congenital anomaly/birth defect.
- Is an important medical event – Important medical events may not be immediately life-threatening or result in death or hospitalisation, but may jeopardize the subject or may require intervention to prevent one of the other serious outcomes listed above (e.g., intensive treatment in an emergency room or at home for allergic bronchospasm; blood dyscrasias or convulsions that do not result in hospitalisation; or development of drug dependency or drug abuse).

#### 12.1.3 Unexpected adverse reaction

An unexpected adverse reaction is an adverse reaction, whose nature, severity or outcome is not consistent with the applicable medicinal product information i.e. the Investigator's Brochure.

### 12.2 Overdose

In case of voluntary or involuntary overdose, it is recommended to carefully monitor the signs and symptoms. As there is no antidote for SENS-401, intensive care admission should be considered according to clinical status, and the treatment would be the standard one for unspecific drug intoxication, including general support which may include immediate gastric lavage within the first hour after intake to diminish the amount absorbed, continuous monitoring

of vital signs, supportive care for cardiovascular function, respiratory aid in case of compromise, electrolyte balance and other measures as clinically indicated.

### 12.3 Pregnancy

If a female participating in the study becomes pregnant during the study (positive pregnancy test after 1 dose), the investigator must stop the treatment and notify it as a Serious Adverse event.

The occurrence of a pregnancy of a partner of a trial subject discovered during the study (start pregnancy after 1st dose) or within 10 days after last administration of the IP is to be communicated to the Sponsor in an expedited manner with the same procedure and timelines as for serious adverse events, independently from the occurrence of an AE.

In all cases, the investigator will contribute to the pregnancy follow-up.

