### 7.5 Number of subjects and duration of study participation

It is planned to enroll a total of 301 or less patients in the study.

Part 1: 111 patients will be enrolled (37 in the placebo arm; 37 in SENS-401 29mg arm, 37 in SENS-401 43.5mg arm)

Part 2: 190 patients will be enrolled (95 in the placebo arm; 95 in selected-dose SENS-401 arm; and approximately 10 in the non-selected dose SENS-401 arm)

Each patient's participation in the study will be 12 weeks:

- 1 to 4 days screening
- 28 days of double blind treatment
- A follow up with no investigational product until 84 Days after inclusion.

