#### 7.6 Determination of end of clinical trial (all patients)

The first part of the study will be considered complete when all patients randomised in Part 1 have completed all the scheduled procedures as described in the flow chart ([Section 4](#)). Any withdrawal from treatment during the 28-day treatment period will be considered as treatment discontinuation.

The end of trial will be considered after the last subject last visit.

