### 8.1 Inclusion criteria

1. Male or female
2. Aged at least 18 years old
3. Patients with unilateral idiopathic sudden sensorineural hearing loss or unilateral/bilateral acute acoustic trauma leading to SSNHL defined by both:
  - 3.1. At least 1 hearing threshold of 50 dB or more among the 3 most affected contiguous frequencies on pure tone audiometric air conduction testing performed 24 hours or less prior to first study treatment), and
  - 3.2. Mean hearing loss of 30 dB or more, averaged across the 3 most affected contiguous frequencies on pure tone audiometric air conduction testing (PTA: Pure Tone Average) performed 24 hours or less prior to first study treatment), compared with the unaffected contralateral ear or reference values from a pre-existing audiogram (dated less than 2 years)
4. Patients with sudden hearing loss with onset within 96 hours prior to prior to first study drug intake.
5. Females must meet 1 of the following: Postmenopausal defined as 12 consecutive months with no menses without an alternative medical cause or Surgically sterile or Abstinent or Practicing **highly** effective birth control (must agree to use 2 forms of contraception [1 of which must be a barrier method]) (Appendix 4) and willing to continue to use **highly** effective contraception for the duration of study participation and for 30 days after the final dose of study drug). Women of childbearing potential must have a negative pregnancy test at screening before the first dose of study drug is taken. Women of childbearing potential are defined as any female who has experienced menarche and who is not permanently sterile or postmenopausal.
6. Male subjects and their female partner(s) must agree to use highly effective contraception (must agree to use 2 forms of contraception [1 of which must be a barrier method]) (Appendix 4) for the duration of study participation and for 90 days after the final dose of study drug.
7. Signed and dated written informed consent.

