## 9 TREATMENT

### 9.1 Investigational Product

SENS-401 14.5 mg tablets (10 mg free base), with a matching placebo

Doses in Part 1:

- 29 mg dose group: 2 tablets of 14.5 mg SENS-401 and 1 tablet of matching placebo twice daily (morning and evening), oral route
- 43.5 mg dose group: 3 tablets of 14.5 mg SENS-401 twice daily (morning and evening), oral route
- Placebo group: 3 matching placebo tablets twice daily (morning and evening), oral route

Doses in Part 2:

- 29 mg dose group: 2 tablets of 14.5 mg SENS-401 and 1 tablet of matching placebo, twice daily (morning and evening), oral route. Depending upon the final dose selected, if this dose is the non-selected dose, it will be stopped immediately after the decision is taken
- 43.5 mg dose group or 3 tablets of 14.5 mg SENS-401, twice daily (morning and evening), oral route. Depending upon the final dose selected, if this dose is the non-selected dose, it will be stopped immediately after the decision is taken
- Placebo group: 3 matching placebo tablets twice daily (morning and evening), oral route

Duration: Given for 28 days.

Administration Route: The tablets must be swallowed with water

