## 11 STUDY PROCEDURES

### 11.1 Visits

Study procedures are described in the flow chart (Section 4). The following are general guidance relating to all visits.

Every attempt should be made to complete the follow-up visits during the defined window periods.

A final follow-up visit is required for all patients. In the rare cases the End of Study Visit (V6) cannot occur, any attempt to contact the patient should be recorded on a special contact form, until/unless appropriate information is obtained which will allow completion of final follow-up visit in the e-CRF, even after the anticipated timeframe.

Blood is collected by venipuncture. The exact time of sample collection should be transferred into database and should be collected on the laboratory request form for local blood sampling.

Important note: Any abnormal laboratory value, abnormal ECG parameter, SAE will be immediately rechecked for confirmation before making a decision of permanent discontinuation of IP for the concerned patient.

Patients will be advised to avoid skin exposure to strong sunlight and to wear sunglasses in bright sunlight for the duration of the study and for 1 week after the last dose.

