#### **11.1.6 Visit 6 End Study visit (Day 84±3)**

The following tests and procedures will be performed at Visit 6 and in the case of premature withdrawal during the study (i.e. prior to Visit 6):

- Inquiring about adverse event and fill an adverse event form if any
- Checking for concomitant medication
- Physical examination including weight and evaluation of main body systems/regions,
- Vital signs: supine blood pressure and heart rate, temperature
- Otologic examination and tympanometry
- Audiometric tests: Pure tone audiometry and OAE tests (optional)
- Word and Speech recognition Tests
- Pregnancy test (for WOCBP)

The patient will be asked to complete specific questionnaires:

- Tinnitus and Vertigo Severity (NRS)
- QoL: EQ-5D-5L
- TFI

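### Partner-pregnancy reporting (protocol 12.3) can end before the 90-day male contraception period does: nominally by 34 days if *the study* means the subject's own participation; a minor safety-reporting mismatch

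*Protocol*

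**What the plan says.** - **Reporting rule.** Protocol 12.3 asks for expedited notification, on SAE timelines, of a "pregnancy of a partner of a trial subject discovered during the study" (with the pregnancy starting after the first dose) "or within 10 days after last administration of the IP". The trigger is the date of discovery.
- **Contraception rule.** Protocol 8.1, criterion 6, requires male subjects and their partners to use highly effective contraception "for the duration of study participation and for 90 days after the final dose of study drug". This governs the date of conception.
- **Dosing.** Protocol 9.1: "Duration: Given for 28 days".
- **Individual follow-up.** Protocol 7.5: "A follow up with no investigational product until 84 Days after inclusion". Visit 6 has a window of ± 3 days.
- **End of trial.** Protocol 7.6: "The end of trial will be considered after the last subject last visit". Section 14.5 says the same for the entire trial.
- **Use of the term for one subject.** Protocol 11.1.6 lists procedures for Visit 6 and "in the case of premature withdrawal during the study (i.e. prior to Visit 6"). Here the phrase refers to one subject's time in the study.

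Section 12.3 does not say which sense of *the study* it intends.

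**The concern.** The sponsor chose 90 days as the period after dosing in which conception by a male subject's partner should be avoided. A protocol that treats those days as needing precaution would be expected to collect the pregnancies that occur in them. Section 12.3 does not clearly do so: a site that follows it to the letter may have no duty to report a partner pregnancy conceived while contraception is still required.

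The rules for women do not have this problem. Criterion 5 asks for contraception until 30 days after the final dose (28 + 30 = Day 58), and pregnancy testing continues to Visit 6 at Day 84. For women who complete, monitoring outlasts the precaution period; for men, reporting may stop before it.

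What is at stake is the completeness of pregnancy-outcome data for a new compound. The primary analysis, type I error and sample size are not touched.

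**Working it through.** **Inputs.** Nominal last dose Day 28 (9.1); contraception to 90 days after last dose (8.1, criterion 6); Visit 6 at Day 84 ± 3 (11.1.6); Visit 5 at Day 28 ± 3 (11.1.5), used here as the range for last dose; 10 days after last IP (12.3); 190 subjects in Part 2 (7.5); failure rate below 1% per year with correct use (Appendix 3).

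**The plan's own figure.** 28 days of treatment plus 8 weeks of follow-up: 28 + 8 × 7 = 84 days, or 12 weeks, which agrees with 7.5.

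**Participation reading.** Uncovered days = (last dose + 90) − max(end of participation, last dose + 10).

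| Case | Calculation | Uncovered days |
|---|---|---|
| Nominal completer | 118 − max(84, 38) | 34 |
| Last dose Day 28, Visit 6 on Day 87 or Day 81 | 118 − 87; 118 − 81 | 31; 37 |
| Last dose Day 25, Visit 6 on Day 87 | 115 − 87 | 28 |
| Last dose Day 31, Visit 6 on Day 81 | 121 − 81 | 40 |
| Dosing stops Day 14, followed to Day 84 | 104 − 84 | 20 |
| Dosing stops Day 1, followed to Day 84 | 91 − 84 | 7 |
| Leaves the study at last dose | 90 − 10 | 80 |

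For a completer the 10-day limb ends at Day 38 and adds nothing. The 80-day case should be uncommon, because 11.1 states: "A final follow-up visit is required for all patients".

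**Whole-trial reading.** Take a subject enrolled *k* days before the last subject, with the last subject finishing on Day 84. Reporting runs to Day 84 + *k* on that subject's own clock, so the gap is 118 − (84 + *k*) = 34 − *k* days, and zero from *k* = 34.

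**Does another rule fill the gap?** The SAE rule in 12.4.2 runs to 30 days after the last treatment day, 28 + 30 = Day 58. It does not address an uncomplicated partner pregnancy after that. The duty in 12.3 to contribute to pregnancy follow-up helps only once the pregnancy is known to the site.

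**Expected events, participation reading.** Count all 190 Part 2 subjects as men with fertile partners, which is an upper bound because the documents give no sex split, and take the 1% limit: 190 × 34/365 × 0.01 = 0.18 conceptions in the nominal 34 days.

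The rule depends on discovery, so some conceptions shortly before Visit 6 can also be missed. The documents give no recognition lag. If it is assumed to be 14 to 42 days, the uncovered conception period becomes 48 to 76 days, and the figure 190 × 48/365 × 0.01 = 0.25 to 190 × 76/365 × 0.01 = 0.40.

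**The case against.** **The term *the study* may mean the whole trial.** The protocol speaks of a patient's participation when it means one subject (7.5, criterion 6), and 12.3 does not use that term. This stands as a reason not to treat the participation reading as settled. Two points still favour it. Section 11.1.6 uses the phrase for a single subject. On the whole-trial reading the 10-day limb does almost no work, since last dose plus 10 days falls well before the last subject's last visit for practically everyone. On either reading some gap remains.

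**Nothing requires the two windows to match.** This is true: one is a precaution for subjects, the other a reporting duty, and neither document says they must be equal. The argument for aligning them rests on the sponsor's own choice of 90 days.

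**The risk is small.** This also stands. Section 5.3.3 reports no specific concern from reproductive toxicology with the racemate, and negative genotoxicity studies. Women are eligible, not every man will have a fertile partner, and criterion 6 asks for two forms of contraception, so the true figure should be below the upper bound.

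**The consent form may cover it.** Its pages were not available here and may already ask male subjects to notify the site. That would narrow the practical gap but leave 12.3 as written.

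**Stronger readings that a reader might infer.** One is that at least 34 days are always uncovered. The documents do not support this: 34 is the nominal value, visit windows alone bring it to 28, and early stopping with continued follow-up brings it lower. Another is that one or more pregnancies will be missed. That needs a contraceptive failure rate well above the Appendix 3 limit, and the documents give none.

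**Conclusion.** The mismatch is real and minor. On the participation reading, which is the better supported but not certain, it is nominally 34 days for a completer, about 28 to 40 days within visit windows, less after early stopping with continued follow-up, and up to 80 days for a subject who leaves at the last dose. On the whole-trial reading it affects only subjects enrolled in about the last 34 days of recruitment.

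Well under one pregnancy is expected. The 0.18 assumes correct contraceptive use at the 1% limit and every Part 2 subject a man with a fertile partner; the assumed recognition lag does not change that conclusion. No efficacy result is affected. The point is worth correcting because the remedy is so cheap.

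**What to change.** Reword section 12.3 to require expedited reporting of any partner pregnancy conceived from the first dose to 90 days after the last dose, whenever it is discovered. Add a reminder to male subjects at Visit 6, or at the early-termination visit, to tell the site of any such pregnancy. The uncovered period then becomes zero, and the meaning of *the study* no longer matters.

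Section 14.4 already commits the sponsor to a substantial amendment and an updated consent form before Part 2, so the change can go there. The cost is one sentence, a reminder at an existing visit and brief site training; no visit is added. The downside is a small amount of pregnancy reporting and follow-up after study end. The change mainly serves Part 2, because it cannot help Part 1 subjects whose 90 days have already passed. If the consent form already asks men to notify the site, only 12.3 needs to change.

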### 12.4 Reporting of adverse events

#### 12.4.1 Adverse events

Any AE occurring after the patient has signed the informed consent must be fully recorded on the patient's e-CRF. The AE form should be supported by a complete documentation available in the patient's file.

Any abnormal laboratory test or ECG considered medically meaningful (e.g., causing the patient to withdraw from the study, requiring treatment or causing apparent clinical manifestations, or judged medically relevant by the investigator) should be reported as an AE. The test should be repeated as soon as possible for confirmation. The AE should be fully described along with start and stop dates, severity, relations to the investigational product, action taken and outcome in the AE form.

For any adverse event, the investigator has to follow-up the case to determine the outcome of the adverse event. He should also try to get all necessary information to assess whether the AE meets the criterion definition of a non-serious or a serious adverse event (SAE). In the later case, it will trigger immediate notification to the Sponsor (see below). Whichever the seriousness criterion, follow-up of the AE is requested until final outcome in case of ongoing adverse event or ongoing complication even after the treatment is discontinued.

Final outcome includes complete resolution or stabilization at a level acceptable to the investigator and the Sponsor. For subjects withdrawn from the study treatment and subjects experiencing AE at the end of the study and within 30 days following the last treatment day, the investigator will manage the appropriate follow up (if required until the AEs are resolved or attributed to a cause other than the study drug).

#### 12.4.2 Serious adverse events

SAEs or suspected adverse event must be reported on the specific SAE form. This SAE form must be completed and forwarded to the designated CRO immediately and no later than 24 hours of learning of the event.

**The Sponsor will ensure that all legal reporting requirements are met.**

**The initial report must be as complete as possible, including all details of the current illness and (serious) AE, and an assessment of the causal relationship between the event**

### **and the study medication.**

**The serious adverse event or medically important event should be fully documented. All additional information not available at the time of the initial report (e.g., AE end, date laboratory values received after the report) must be reported on a follow-up SAE form and transmitted to the designated CRO as soon as possible.**

Whatever relationship to the study drug any serious adverse event occurring within **30** days following the last treatment day must be reported.

An inquiry will then be conducted by the designated CRO in order to determine whether the event was caused by the treatment to make all necessary submission. In any case, and as a conservative measure, Sensorion will re-assess only cases that were considered not related to the study drug by the investigator.

Sensorion (or designated CRO) will inform the Health Authorities and the Ethics Committees/IRB in writing in accordance with current regulations.

#### **12.4.3 Severity and causality of events**

The Investigator should assess any event with regard to its severity and causality.

The severity of the adverse events is determined in the following manner:

- mild: no interference with the subject's daily activities
- moderate: moderate interference with the subject's daily activities
- severe: major and unacceptable interference with the subject's daily activities

Both the investigator and the sponsor will assess the possible relationship between the adverse event and the study drug:

- **Unrelated**: Unrelated adverse events are those that are judged to be not related to the study or to the study drug by the investigator and the sponsor.
- **Probable**: assuming a causal relationship;
- **Possible**: a causal relationship cannot be excluded
- **Unlikely**: a causal relationship with another origin is more likely Unrelated;
- **Not assessable**: impossible to assess, because of insufficient evidence, conflicting data or poor documentation.

Any adverse event for which, either the Investigator or the Sponsor considers that a causal link with the study product could reasonably be envisaged, is considered a suspected adverse effect. Both the Sponsor and the Investigator's assessment with regard to causality will be reported in the declaration of suspected adverse effect. In no case Sensorion will provide a downgrade relationship as compared to the investigator's assessment.

